10.1. Suspension or Early Termination of Study

The study or a site may be suspended or terminated early by the Sponsor, IRB or regulatory body, including but not limited to issues with safety, disease management, and unethical conduct. Should this occur, all participants currently participating in the trial will be notified, will be withdrawn safely from the study, and will resume their usual NIPPV therapy.

11. SAFETY

The investigator is responsible for monitoring the safety of subjects enrolled into the study at the study site. The investigator or qualified designee will enter the required initial and follow-up information regarding adverse events on the appropriate eCRF within the EDC system. Investigators are responsible for following all serious adverse events (SAEs) until resolution, stabilization, or the event is otherwise explained, and to report serious adverse events as well as serious injury or death that were related to (caused by or contributed to) the Astral study device in accordance with their local IRB requirements. Investigators should follow usual clinical practice at their institutions for reporting serious events to the regulatory authorities.

11.1. Definition of Adverse Events

11.1.1. Adverse Event (AE)

Any untoward medical occurrence in a patient or clinical investigation subject administered a medical product and which not necessarily have to have a causal relationship with this treatment.

11.1.2. Unanticipated Adverse Device Effect

Unanticipated adverse device effect is any serious adverse effect on health or safety, any life-threatening problem or death caused by, or associated with a device, if that effect, problem, or death was not previously identified in nature, severity, or degree of incidence in the application; or any other unanticipated serious problem associated with a device that relates to the rights, safety, or welfare of subjects.

11.1.3. Serious Adverse Effect (event or reaction) (SAE)

Any untoward medical occurrence that:

- results in death
- is life-threatening
- requires in-patient hospitalization or prolongation of existing hospitalization (voluntary hospitalizations for elective surgeries are not considered as serious adverse events)
- results in persistent (symptomatic or moderate) or significant disability /incapacity
- an important medical event; or
- is a congenital anomaly/birth defect

All known details of the SAE will be sent to the Principal Investigator and Sponsor within 24 hours. Together the PI and Sponsor will determine whether the SAE may be device related and whether it is safe for the trial to continue. The PI and Sponsor will determine if the SAE requires reporting to the IRB, and will follow the SAE to completion.

12. STATISTICAL ANALYSIS

Data recorded during 'Ramp' time (i.e. the time taken for the pressures to increase to the prescribed settings when the device is first turned on) will be excluded. Data will be checked for normality. If the data is normally distributed, descriptive data will be presented as mean and standard deviation (SD), and marginal differences. Comparisons between the two modes will be done using paired T-test.

If the data is not normally distributed, descriptive data will be presented as median and interquartile range (IQR). Comparative analysis between AutoEPAP and manual EPAP will be performed using the Mann-Whitney U test.

A $p < 0.05$ will be considered significantly different between AutoEPAP and manual EPAP if: 1. there is no significant difference between AutoEPAP and manual EPAP or 2. AutoEPAP is significantly better than manual EPAP, than the null hypothesis will be rejected and the AutoEPAP algorithm will be considered as 'passed'.

We pre-specify a non-inferiority margin for ODI4% of 2 per hour and specify a statistical test for non-inferiority as:

Non-inferiority margin for ODI: $d=2$

H0: $\mu_A - \mu_B \leq -d$ (new algorithm is inferior)

H1: $\mu_A - \mu_B > -d$ (new algorithm is non-inferior)

To show non-inferiority the lower bound of the 95th confidence interval of the difference between the groups must not cross the margin boundary (ODI4% of 2 per hour).

Which will be tested with a single-sided t-test with an alpha of 0.05 and a power of 80%. This pre-specified non-inferiority margin for ODI4% of 2 per hour is considered clinically unimportant, is the same margin as used in a previous study [26], and 2 per hour represents approximately 7% of severe UAO (30 per hour).

We also pre-specify that we will reject subjects where the ODI4% cannot be controlled during the control arm phase (manual EPAP). This is defined as an ODI ≥ 10 per hour. This process will be documented in the study Manual of Procedures and training provided for all participating sites.

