3. PROTOCOL SUMMARY

Objectives	The objective of this study is to evaluate AutoEPAP versus manual EPAP in iVAPS mode on the Astral device.
Study Design	This will be a prospective, multi-center, single-blind, randomized, cross-over design. The study will occur in a lab/hospital setting. Eligible subjects that represent patients with respiratory failure will complete two PSG study nights.
Number of Subjects	Up to 40 subjects overall will be randomized to obtain endpoint data on at least 36 evaluable subjects. This accounts for the expected dropout rate (10%).

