6.2.4. Sample Size Justification

This study is powered for demonstrating ODI4% non-inferiority between the AutoEPAP algorithm and manual EPAP algorithm on the Astral device.

This protocol has been powered with the following inputs based on a previous study [26].

Expected mean difference in ODI: 0
 Expected standard deviation in ODI: 1.55
 Power = 80%
 Alpha = 0.05

Power to detect a difference of 1 per hour using a paired two-tailed t-test:

$$n = (Z\alpha + Z\beta)^2 \times (SD/difference)^2 = 22.84 = 23$$

Therefore, based on a crossover non-inferiority hypothesis test (one in which the outcome is dependent) we can be 95% sure that a sample size of 23 is sufficient to detect inferiority of AutoEPAP compared to with manual EPAP with respect to difference of ODI.

The update to this protocol (v3.0 to v4.0) was completed to be consistent with the recent FDA clearance of Astral with iVAPS. The increase in enrollment goal will provide additional power (95%) to detect a difference between AutoEPAP and manual EPAP.

We pre-specify a non-inferiority margin for ODI4% of 2 per hour (refer to Section 12). Basing the sample size on being able to detect the smallest difference in ODI (1 per hour) will provide greater power, through a larger sample size, in testing the non-inferiority margin (2 per hour).

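### Protocol Section 12 gives two different success rules for AutoEPAP without saying which governs, and the SAP applies only one of them without withdrawing the other

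*Protocol*

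**What the plan says.** Protocol Section 12 contains two decision rules for the comparison of AutoEPAP with manual EPAP.

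- **Rule 1 (difference test).** The rule, at p < 0.05, applies where "there is no significant difference between AutoEPAP and manual EPAP or 2. AutoEPAP is significantly better than manual EPAP". In either case the section declares the null rejected and gives AutoEPAP a pass. The test is a paired t-test if the data are normal. If they are not, "Comparative analysis between AutoEPAP and manual EPAP will be performed using the Mann-Whitney U test".
- **Rule 2 (non-inferiority).** The margin is d = 2/h, with "H0: $\mu_A - \mu_B \leq -d$ (new algorithm is inferior") and the reverse as H1. The criterion reads: "To show non-inferiority the lower bound of the 95th confidence interval of the difference between the groups must not cross the margin boundary". The test is one-sided at 0.05. A and B are not defined.

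Protocol Section 6.2.4 states the purpose as "This study is powered for demonstrating ODI4% non-inferiority between the AutoEPAP algorithm and manual EPAP algorithm on the Astral device", yet calculates the sample size from a two-tailed paired t-test for a difference of 1/h.

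SAP Section 6 states only a non-inferiority hypothesis and places inferiority above +d. SAP Section 6.1 tests it with a one-sided paired t-test against 2/h and adds an upper one-sided 95% bound. SAP Section 4 drops normality testing. The SAP mentions neither Rule 1, nor Mann-Whitney, nor the −d and lower-bound wording, and it does not say that it supersedes Section 12.

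**The concern.** Rule 1 treats failure to find a difference as proof of acceptability. A non-significant result does not show that the difference is below 2/h, and a significant one does not show that it is above 2/h. The rule therefore does not answer the question the trial says it is powered for.

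The fallback adds a design error. Each subject contributes one night on each setting, and Mann-Whitney U treats the two nights as independent groups. Under Rule 1 a difference missed for that reason counts as a pass.

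Rule 2 has an open direction. A higher ODI is worse, so inferiority of AutoEPAP lies on the positive side of AutoEPAP minus manual. The −d and lower-bound form is coherent if A is manual EPAP and reversed if A is AutoEPAP. The SAP names AutoEPAP first when it defines the paired difference.

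At stake is the primary verdict. The two rules can disagree on the same data, and a reader holding both documents could defend either result afterwards.

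**Working it through.** **Inputs**

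- Expected difference 0 and SD 1.55 (Protocol 6.2.4: "Expected mean difference in ODI: 0"). The protocol calls 1.55 the SD in ODI. I take it as the SD of the paired differences, which is how its formula uses it.
- n = 36 evaluable (Protocol Section 3: "Up to 40 subjects overall will be randomized to obtain endpoint data on at least 36 evaluable subjects"), with n = 23 (the calculated size) and n = 40 (all randomized) alongside.
- Margin 2/h, one-sided 0.05. Rule 1 is modelled as not significantly worse on a two-sided 0.05 paired t-test.

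**The plan's own figures.** The printed formula, (z_α + z_β)² × (SD/difference)², gives (1.960 + 0.842)² × 1.55² = 18.86, so 19, two-sided, and 14.85, so 15, one-sided. With the t distribution the sizes are 21 and 17. These match SAP Section 10, not the protocol's 22.84. The stated 95% power after the enrollment increase is about right: the two-sided paired t-test at n = 36 and 1/h gives 96.4%. Nothing below depends on the 23 being correct.

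**Step 1: where the rules conflict.** With an observed SD of 1.55, Rule 1 passes if the mean difference (AutoEPAP minus manual) is below t(0.975) × SD/√n. Non-inferiority is shown if it is below 2 − t(0.95) × SD/√n. At n = 36, SD/√n = 1.55/6 = 0.258:

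- Rule 1 limit: 2.030 × 0.258 = 0.52/h
- Non-inferiority limit: 2 − 1.690 × 0.258 = 1.56/h

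Any observed mean between the two limits fails Rule 1 and is non-inferior.

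| n | Conflict zone (/h) |
|---|---|
| 23 | 0.67 to 1.45 |
| 36 | 0.52 to 1.56 |
| 40 | 0.50 to 1.59 |

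If the confidence interval in Section 12 is read as two-sided, the upper end at n = 36 is 2 − 2.030 × 0.258 = 1.48.

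**Step 2: how often they disagree** (400,000 simulated trials per cell, SD 1.55).

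| True difference (/h) | n = 23 | n = 36 |
|---|---|---|
| 0 | 2.5% | 2.5% |
| 0.25 | 11% | 15% |
| 0.5 | 31% | 47% |
| 1 | 75% | 95% |

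In effect every disagreement is a Rule 1 failure with non-inferiority shown. At n = 36 and a true 1/h, the noncentral t gives a 3.6% pass rate for Rule 1 and 98.4% for non-inferiority.

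**Step 3: when Rule 1 is the looser rule.** At a true +2/h and SD 1.55, Rule 1 passes about 1 in 10⁸ trials at n = 36 and 4 in 10⁵ at n = 23. It exceeds 5% only if the SD is above 2.54 (n = 23), 2.94 (n = 30), 3.24 (n = 36) or 3.42 (n = 40), which is 1.64 to 2.21 times the planning value. At n = 36 with assumed SDs of 4 and 5, it passes 17% and 35%, against 5% for non-inferiority at any SD.

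**Step 4: direction of Rule 2.** If A is AutoEPAP, a lower one-sided 95% bound above −2 is reached in essentially 100% of trials when AutoEPAP is truly 2/h or 5/h worse, and in 5% when it is 2/h better.

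**Step 5: power of the SAP's test** against 2/h, one-sided 0.05, SD 1.55. At a true difference of 0 it is above 99.9% for n = 23, 36 and 40. At a true 1/h it is 91%, 98% and 99%.

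**The case against.** The strongest reply is that the SAP has already settled the matter. It was written against Protocol Revision 4.0, states one primary hypothesis with inferiority above +2/h, and names one test. By dropping normality tests it removes the trigger for Mann-Whitney. An analyst who follows the SAP has only one test to run. This stands as a description of practice. But the replacement is by silence: where the SAP's author disagreed with the protocol's sample size, Section 10 said so openly, and nothing comparable is said about Section 12.

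Second, the direction fault is conditional. With A as manual EPAP, Rule 2 is coherent, and its printed labels show the intent. That is correct, and it is why A and B must be defined. The near-100% figure applies only to the other reading.

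Third, the harm at the planning inputs is modest: 2.5% disagreement at a true difference of 0, with Rule 1 the stricter rule. That also stands, and it limits the severity.

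Fourth, the Rule 1 sentence is garbled, and treating it as a free-standing two-sided paired t-test is an interpretation. It is the natural one, since the section names a paired t-test and p < 0.05.

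Finally, Section 6.2.4 explains that sizing on 1/h was deliberate, to give more power at the 2/h margin. Rewording its power statements is therefore mostly drafting.

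**Conclusion.** The concern holds and should be fixed. Section 12 contains a decision rule that is not valid for non-inferiority, beside one that is, with no order of precedence. The SAP uses the valid rule without withdrawing the other, its unpaired fallback, or the ambiguous direction.

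The consequence is a primary verdict that can go two ways. AutoEPAP could fail Rule 1 while meeting the trial's own margin, and this becomes likely once AutoEPAP is truly about 0.5/h worse or more but still well inside the margin. At the planning SD, Rule 1 does not let a 2/h-worse device through; it would do so in more than 5% of trials only if the SD were roughly twice the planned value at n = 36. These sizes rest on 1.55 being the SD of paired differences, on normal differences, and on the reading of Rule 1 given above. No size is claimed for the effect of Mann-Whitney.

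**What to change.** 1. Delete the Section 12 sentence that passes AutoEPAP on a non-significant difference.
2. Delete the switch to Mann-Whitney U. If a sensitivity analysis for non-normality is wanted, use a paired method.
3. State one criterion in both documents: AutoEPAP passes only if the one-sided 95% upper confidence bound of the mean paired ODI4% difference, AutoEPAP minus manual, is below 2/h by the SAP's paired t-test.
4. Define A = AutoEPAP and B = manual EPAP. In Section 12 write H0: mean difference ≥ 2 and H1: mean difference < 2, with an upper bound in place of the lower bound. In SAP 6.1 give the difference for the confidence bound as AutoEPAP minus manual EPAP. SAP Section 6 puts the boundary value itself under H1; aligning it is a tidy-up that changes no result.
5. In Section 6.2.4, express power as power for non-inferiority at 2/h: at n = 36 and an SD of paired differences of 1.55, above 99.9% if the true difference is 0 and 98% if it is 1/h.

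The cost is wording in Protocol Sections 6.2.4 and 12 and in SAP Sections 6 and 6.1. It needs no new data and no change in sample size. The sponsor gives up the alternative route to a pass, which at the planning SD is the harder one.

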12.1. Withdrawal of Subjects

Due to factors not able to be predicted prior to the commencement of clinical studies, participants may at times either "drop-out" or withdraw from the study by their own volition, or be withdrawn from the study by the investigator or Sponsor. Data from participants who are excluded, drop-out or withdraw from the study prior to study completion will be collected until the point of study discontinuation, unless the participant explicitly withdraws his/her data. Where participants formally revoke their consent, which includes the revocation of consent for any data collection, all data collected from these participants will not be used in any data analyses.

All efforts will be made to follow-up on the collection of missing data. If collection of missing data is not possible, all enrolled participants' remaining collected data will still be included in the final data set for analysis on the condition that the participant has completed all required study-related procedures. Enrolment is considered as taking place at the point of randomization.

13. DATA MANAGEMENT AND STORAGE

13.1. Data Collection

All raw data from the study will be non-identified format and documented on:

- CRF's (Appendix C)
- Sleep study reports (which details sleep and respiratory variables and therapy settings)
- Flash drives from the devices.

13.2. Study Documentation

Throughout the conduct of the study, all required data will be entered into the eCRF for each subject. The investigator should ensure the accuracy, completeness, and timeliness of the data reported to the Sponsor in the eCRFs and in all required reports and will be asked to sign and date the appropriate eCRF page(s) to verify the data collected. Data entered into the eCRF must be consistent with source documents. Any change or correction to an eCRF will be captured in the EDC system audit trail.

The clinical site will provide study data to the Sponsor by recording data in the EDC System (21 CFR Part 11 compliant).

In cases of subject-reported data, the eCRF will be the source record.

The site PI or designee and the clinical monitor will review completed eCRFs for accuracy, discrepancies, and missing information. The information entered into the eCRF will be accessible to the appropriate ResMed Medical Affairs personnel.

13.3. Query Generation

Any data queries will be sent to site for reconciliation via the eCRF system and final close-out will be from the study monitor.

13.4. Data Storage

All electronic systems used by the site and Sponsor will have adequate security to protect patient privacy and data integrity. All paper documentation will be locked in a secured cupboard. All trial data and documentation will be retained for a minimum of 15 years before it is destroyed. Access to data maintained in the EDC System is strictly limited to authorized personnel.

13.5. Inspection of Records

Periodically the Sponsor or representative will review the Investigator study file and the study data to verify compliance with applicable regulations and the protocol, and to verify accuracy of the data.

13.6. Study Files and Record Retention

The investigator must maintain adequate and accurate records as specified in Essential Documents for the Conduct of a Clinical Trial (E6, Section 8 of the ICH Guideline for GCP) to enable the conduct of the study to be fully documented and the study data to subsequently be verified. These documents should be classified into two separate categories: (1) investigator's study file and (2) subject clinical source documents.

Essential documents must be retained until at least 2 years after notification by the Sponsor that the investigations have been discontinued OR 2 years after the last approval of a marketing application. The investigator must notify the Sponsor prior to destroying any clinical study records.

13.7. Regulatory Documentation

Documents that must be provided to the Sponsor prior to study initiation are:

- Signed, dated current (within 2 years) curriculum vitae of Investigator and Sub-Investigator(s)
- Financial disclosure for physicians and nurses
- Signed (original), dated Investigator Agreement
- Assurance that the IRB complies with requirements set forth in Title 21 Part 56 of the Code of Federal Regulations. The required documentation consists of name and address of the IRB, a current list of members including title, gender, occupation and any institutional affiliation of each member. A general assurance number from the Department of Health and Human Services may be substituted for this list.
- Written notification (copy) to the Investigator from the IRB approving the protocol
- IRB approved informed consent (copy) and any other adjunctive materials to be used in the study as required.

13.8. Distribution of Results

Data analyses will be completed by an independent statistician and the clinical study report will be completed by the Sponsor.

Any published and presented data will be non-identifiable.

14. ETHICAL CONSIDERATIONS

14.1. Institutional Review Board (IRB)

The investigator must have written and dated approval from the IRB for the protocol, consent form, subject recruitment materials/process (advertisements), and any other written information to be provided to subjects. The investigator should also provide the IRB with a copy of the product labeling information and any updates. The investigator will provide the IRB with reports, updates, and other information (e.g., safety updates and protocol amendments) as required by regulations.

14.2. Protocol Deviations

An investigator is required to conduct this study in accordance with the signed Investigator's Agreement, this Investigational Plan, applicable laws and FDA regulations, and any conditions of approval imposed by the reviewing IRB and FDA. According to FDA regulation 21 CFR § 812.150(a)(4), an investigator shall notify the sponsor and the reviewing IRB of any deviation from

the investigational plan to protect the life or physical well-being of a subject in an emergency. Such notice shall be given as soon as possible, but no later than five working days after the emergency occurred. Except in such an emergency, prior approval by the sponsor is required for a change in or deviations from a plan and, if these changes or deviations could affect the scientific soundness of the plan or the rights, safety or welfare of human subjects, FDA and IRB approval may also be required in accordance with 21 CFR § 812.35(a).

14.3. Risk Analysis

14.3.1. Non-Significant Risk Determination

The Astral device with the iVAPS algorithm has been cleared (K152068) by the FDA to provide therapy to patients who require mechanical continuous or intermittent ventilation. The device is intended for home and hospital use. The purpose of this study is to evaluate the effect of a new algorithm that auto titrates EPAP to treat patients with UAO and respiratory failure.

Clinical personnel will observe the subject on the fitting and use of all Astral devices. They will monitor the subject's clinical parameters and will intervene, if required.

As per FDA good practice guidelines (21 CFR 10.115), this study protocol as well as the Astral device was assessed for risk to participants. As this study does not meet the definition of significant risk as defined by 21 CFR 812.3(m), the investigative team has determined that this protocol and the Astral device is non-significant risk. All subjects will maintain all other therapy regimens per standard clinical care; this protocol does not dictate any other adjustments to the participants' care regimen and there are no protocol-required assessments or procedures that pose significant risk to the participants. As required by the FDA, the IRB(s) will review this study protocol and make the final determination of NSR designation.

Subjects should be encouraged to discuss any issues they are having with therapy during the study. The investigator should assess for changes in the health or well-being of the subject in response to general, non-directed questioning (e.g., "How are you feeling while using the therapy?"). Side effects should be documented on the site's source documents. Any transient side effects, at a minimum, should be documented in the clinic record.

Furthermore, if during the evaluation the subject believes the mask or therapy is intolerable, the study staff will be instructed to discontinue use of the protocol device on the patient and ensure the patient returns to using their current mask and therapy. Potential expected adverse events are believed to be mild and similar to other commercially available mask systems.

Participants will be asked to use the study device only during the two study visits that are fully attended PSG nights in a sleep lab. The attending technicians have experience setting up the eligible patient population in this study. All subjects return to their current NIPPV therapy after completing the study visits.

As the trial involves a minimally tested algorithm for the treatment of respiratory failure, there is a small chance that treatment will be ineffective and will result in a maximum of one night with suboptimal therapy. This may result in a temporary increase in the participant's CO₂ levels causing dyspnea, tachypnea, flushing, and/or sweating. This is being mitigated in two ways:

1. Trained study staff are able to stop the study and resume normal treatment at any time if they feel the patient requires more effective treatment.
2. Participants' oxygen and carbon dioxide levels will be monitored overnight using oximetry and transcutaneous CO₂ monitoring equipment (as per routine practice), to ensure further medical treatment is not required for hypoxia or hypercapnia.

Potential expected adverse events are believed to be mild and similar to other commercially available NIPPV systems. The anticipated adverse effects during this trial are minimal and limited to those recognized with standard use of NIPPV treatment. These include:

- drying of the nose, mouth, or throat
- nosebleed
- bloating
- ear or sinus discomfort
- eye irritation
- skin rashes on the face from the mask

Eligible patients will already be established on NIPPV treatment (ST or VAPS mode). It is expected that any anticipated adverse events linked to AutoEPAP in iVAPS mode will be similar to ST or VAPS modes.

